## PROTOCOL

### Background

#### 1. Provide the scientific background, rationale and relevance of this project.

##### INSTRUCTIONS

- This should include a referenced systematic evidenced-based review when possible.
- If this study involves qualitative research explain the major constructs of your study.
- Do not state in this section what you plan to do in this study. This information should be entered later under “What will be done in this protocol?”
- Do not include the bibliography in this section.
- For studies submitted under the Expedited review criteria, this section need not be more than a few paragraphs.
- For those studies where data will be analyzed collaboratively by multiple sites doing a similar study for which there is no common protocol (Collaborative Site Analysis Study) include a description of the common scientific goals/ procedures/data points.
- If this is an update to current templates from Protocol Builder make sure the information throughout the protocol includes the most current information.

Answer/Response:

- includes the most current information.

The scope of the healthcare challenge posed by stroke is massive, both in the number of affected persons and the related cost burden. There were an estimated 892,300 stroke-related hospitalizations in the U.S. in 2005, representing 77.3 stays per 10,000 persons over 45 years of age [1]. Approximately 50% of these individuals suffer from chronic deficits in UE function [2]. As the leading cause of disability in the U.S., the long-term financial impact of stroke is exorbitant. From 2005 to 2050, the total stroke-related burden on the U.S. economy is expected to exceed \$2 trillion, including costs due to hospitalization, rehabilitation, nursing home stays, outpatient care, medications, and lost earnings [3].

Modern stroke rehabilitation practice is based on the principle of brain plasticity – the formation of new circuits and changes to internal structures that remap existing synapses to perform functions previously accomplished by injured cortical tissue [4]. Plasticity may strengthen redundant pathways to restore lost functionality, in effect remodeling the lesioned brain [5]. This process requires that the affected neurological pathways be exercised through interactions that involve the stroke-impacted functions [6], [7]. Consequently, research suggests that intensive, repetitive, task-directed therapy can encourage the desired cortical plasticity [8], [9], [10]. Training specificity is also an important component, whether targeting specific functional movements (e.g. squeezing a tube of toothpaste) or an integrated skill (e.g. self-grooming) [11], [12]. Repetitive ADL practice, by definition, satisfies these critical requirements for brain plasticity supporting UE recovery.

Weakness in grip strength and finger extension are leading causes of hand motor control deficits following stroke [13]. In particular, a loss of ability to extend the fingers is a key indicator for poor grasping performance [14]. Additionally, an inability to bring the hand and wrist into a neutral pose can

prevent participation in the task-directed functional practice necessary for neuroplasticity to occur. A common technique to enable stroke patients to achieve a functional hand pose (and thus participate in rehabilitation) is a dynamic splint that supports finger and/or wrist extension. When larger forces are necessary (i.e. to overcome abnormal muscle tone), an outrigger-type splint may be employed. One example is the spring-based SaeboFlex system [15]. For patients lacking finger extension due to weakness or mild hypertonicity, a low profile device such as the SaeboGlove [16] is preferable. SaeboGlove () is a commercially-available, passive glove orthosis that employs a plastic splint to support the wrist and a rubber band-based tensioner system to support finger extension and enable patients to engage in task-specific training. These Saebo products are used in over 2,000 clinics and hospitals (and by 10,000 trained clinicians) worldwide.

Numerous past efforts to apply technology to hand therapy have focused on the use of active assistance including cables, pneumatics, and robotics [17], [18], [19], [20], [21], [22], [23] [24]. The cost of these complex systems is typically very high, and many never find application beyond the research laboratory. On the other end of the spectrum are adaptations of hand tracking systems for therapy that do not provide any assistance to the wrist, hand, or fingers [25] [26] [27]. Hand movements elicited by these tracking system games are not ADL-oriented and experiences do not correlate to real-world tasks, which is a central tenet of brain plasticity. In summary, previous systems are limited by: (1) not providing the finger extension and wrist support necessary to enable a stroke patient to bring the hand and wrist into the neutral position required for functional tasks; (2) limitations of sensor and software design that do not permit hand or arm involvement in virtual practice of ADLs; and (3) childish arcade-type user experiences do not involve mental imagery and cognitive challenges that are representative of real-world activities.

Although there is substantial literature on adaptations of “virtual reality” for rehabilitation [28], low-cost commercial sensors and commercial game engine technology have only very recently enabled the development of sophisticated systems at a price point that is compatible with at-home use. Moreover, it is also only recently that researchers have begun to unravel the relationship between game design and patient motivation. Adherence is an essential aspect of any treatment program. A perhaps-obvious, but often-overlooked, reality is that to realize gains through rehabilitation, a patient must accept and adhere to the prescribed treatment regime. The challenge of adherence is compounded by the fact that the intensive, repetitive, task-directed therapies associated with brain plasticity can be mundane, fatiguing, and even painful for stroke patients. Without the direct encouragement of a therapist, adherence is a particular challenge for home-based therapy.

The effectiveness of stroke therapy may be further bolstered by incorporating mental practice of relevant activities [33]. During mental practice of UE motor tasks, neural activation patterns may occur as if the impaired limb were actually performing the intended action [34], [35]. One approach to promoting this effect is by use of a mirror to present the image of an unaffected hand as if it were the paretic one [36]. The resulting enhancement in cortical representation of the impaired extremity appears to lead to tangible improvement in motor function. Empirical evidence of the benefit of mental imagery can, in part, be explained by a

model of cognitive psychology in which subliminal activation of the motor system is embedded in “covert” stages of action that precede actual motor response [37]. These precursor stages encompass visualization of intended outcomes, recognition of environmental factors, and learning by observation – elements that are directly facilitated by task-oriented virtual world-based ADL training. In the virtual world, limitations of impairment can be artificially mitigated, permitting the patients to visualize task completion in the appropriate environmental context, with meaningful tasks that map to real-world experience.

The purpose of this research study is to assess the effectiveness of a novel ADL-centered virtual reality system that is able to incorporate tracking and assistance to the hand for the purposes of stroke rehabilitation. The Glove Rehabilitation Application for Stroke Patients (GRASP) system enhances a commercial glove orthosis, the SaeboGlove (see Figure 1), with finger tracking sensors to enable a patient to manually interact with a virtual environment for UE motor practice.

Figure 1. GRASP sensors on SaeboGlove orthosis

The GRASP system, developed by Barron Associates, Inc., comprises the sensor-enhanced glove orthosis, a Kinect sensor, a Windows 10 computer, and software for virtual world-based practice of activities of daily living. Using the Kinect and the glove sensors, GRASP software tracks a patient's UE movements and translates them into equivalent movements of a graphical avatar that represents the patient in a virtual environment rendered on the computer display monitor. Figure 2 shows examples of virtual activities provided by GRASP software.

[figure not shown]

Figure 2. Virtual Activities of Daily Living (ADLs)

A completed GRASP Phase I study (IRB-HSR 19952) involving use of the GRASP device by 15 stroke patients demonstrated the criterion validity of UE performance measures derived from the system, as well as the usability of the device by the targeted patient population. The results of the completed GRASP Phase I study are documented in the following journal paper.

Adams, R. J., Ellington, A. L., Armstead, K., Sheffield, K., Patrie, J. T., & Diamond, P. T. (2019). Upper Extremity Function Assessment Using a Glove Orthosis and Virtual Reality System. *OTJR: Occupation, Participation and Health*, 39(2), 81–89. <https://doi.org/10.1177/1539449219829862>

The GRASP Phase II study builds on the Phase I results, targeting demonstration of efficacy of a home exercise program (HEP) for UE stroke therapy employing the GRASP system. The GRASP Phase II device has been improved to address lessons learned in the Phase I study. Notably, the glove sensor system is now wireless (Bluetooth) and the GRASP software incorporates a wider range of virtual activities to support practice over an 8-week intervention.

### Objectives/Hypothesis

#### INSTRUCTIONS:

If this study involves biomedical research clearly state the objectives and hypotheses and clearly define the primary and any secondary outcome measures. If this study involves qualitative research clearly state your research hypothesis or question.

This section should not include information already included in other sections such as background information or information from the procedures section.

Answer/Response:

**Objectives:**

- Investigate the efficacy of GRASP therapy for recovery of hand function
- Acquire evidence of system usability and user acceptance

**Hypotheses**

- Use of GRASP for UE practice in a Home Exercise Program (HEP) will improve motor function in a cohort of adult stroke patients
- Subjects assigned to the GRASP HEP will experience improved motor function compared to those assigned to a Usual Care Treatment (UCT) group
- GRASP will be found to be usable and well-accepted by participants who have sustained a stroke.

**Study Design: Biomedical**

**1. Will controls be used?**

Answer/Response:

**YES**

► IF YES, explain the kind of controls to be used.

Answer/Response:

**Half of subjects will be randomized to a UCT group.**

**Half of subjects will be randomized to a GRASP HEP group.**

**2. What is the study design?**

Example: case series, case control study, cohort study, randomized control study, single-blind, double-blind, met-analysis, systematic reviews, other. You may also view the IRB-HSR Learning Shot on this topic to help you answer this question.

[https://hrpp.irb.virginia.edu/learningshots/Writing\\_protocol\\_June09/player.html](https://hrpp.irb.virginia.edu/learningshots/Writing_protocol_June09/player.html)

Answer/Response:

**Rater-blinded randomized control study**

**3. Does the study involve a placebo?**

Answer/Response:

**NO**

► IF YES, provide a justification for the use of a placebo

Answer/Response:

**Human Participants**

**Ages:** 18 years or greater

**Sex:** Any

**Race:** Any

**Subjects- see below**

**INSTRUCTIONS:** For question 1-4 below insert an exact #. Ranges or OPEN is not allowed. This # should be the maximum # you expect to need to enroll (i.e. sign consent) If you are only collecting specimens the number of participants should equate to the # of specimens you need. If you are collecting only data from a chart review the number should designate the number of subjects whose medical records you plan to review. Age/ Sex/Race criteria should designate the demographics of participants from whom you will obtain the specimen/data.

**1. Provide target # of subjects (at all sites) needed to complete protocol.**

**INSTRUCTIONS:** If this is NOT a database protocol, this number should be the same as the number of subjects needed to obtain statistically significant results.

Answer/Response:

**40**

**2. Describe expected rate of screen failure/ dropouts/withdrawals from all sites.**

Answer/Response:

**20%**

**3. How many subjects will be enrolled at all sites?**

**INSTRUCTIONS:** This number must be the same or higher than the # from question # 1 in order to account for the # of screen failures, dropouts, withdrawals described in question # 2.

Answer/Response:

**40**

**4. How many subjects will sign a consent form under this UVA protocol?**

**INSTRUCTIONS:** If the protocol does not have a consent form- the number listed here should reflect such things as the number of subjects from whom specimens will be obtained, the number of charts to be reviewed etc.

Answer/Response:

**40**

### Inclusion/Exclusion Criteria

**INSTRUCTIONS:**

- The inclusion and exclusion criteria should be written in bullet format.
- *This item applicable if the study will require consent (verbal or written).* Unless there is a scientific reason for not recruiting a certain type of vulnerable population(e.g. not enrolling fetuses, neonates or children in a study regarding Alzheimer's) list the following vulnerable populations under either Inclusion or Exclusion criteria below:

pregnant women, fetuses, neonates, children, prisoners, cognitively impaired, educational or economically disadvantaged, non-English speaking subjects.

[figure not shown]
- If you will not enroll subjects who do not speak English because certain procedures cannot be carried out if the subject does not speak English (e.g. a survey is not validated in other languages) insert the following as an Inclusion Criteria: Willingness and ability to comply with scheduled visits and study procedures.
- If this is a collection of only retrospective\* specimens or data, the inclusion criteria must include a start and stop date for when specimens/ data will be collected.
- The stop date must be prior to the version date of this protocol.
- \*Retrospective: all specimens are in a lab at the time this protocol is approved by the IRB. All data exists in medical records or records from previous studies at the time this protocol is approved by the IRB.

### 1. List the criteria for inclusion

Answer/Response:

1. Participant has had a right or left hemispheric stroke affecting normal hand function
2. Participant has sufficient active finger flexion at the MCP joint in at least one finger to be detected by visual observation by a study therapist.
3. Participant has visual acuity with corrective lenses of 20/50 or better.
4. Participant's affected hand fits within sizing available in the SaeboGlove (see Figure 2).
5. Participant must have active movement against gravity of at least 30 degrees shoulder flexion, 45 degrees elbow flexion, elbow extension to within 30 degrees of full extension, and 15 degrees shoulder internal and external rotation.
6. In the opinion of a study therapist, participant can independently and safely use the system at home or has an at-home caregiver who is willing and able to assist.
7. In the opinion of a study therapist, participant has a suitable and safe space in their home for using the GRASP system.
8. Participant is willing and able to provide informed consent.

#### GLOVE LINER MEASUREMENTS:

A.) **Hand Circumference:** measure hand circumference by wrapping tape circumferentially around hand: \_\_\_\_\_

B.) **3rd Finger Length:** measure from tip of 3rd digit to the most distal wrist crease: \_\_\_\_\_

		(A) HAND CIRCUMFERENCE						
		4-5.5.5	5.5-6.5	6.5-7.5	7.5-8.5	8.5-9.5	9.5-10.5	
(B) 3RD FINGER LENGTH	6.0-6.5	XS	XS	XS				
	6.5-7.0	XS	XS	XS	S			
	7.0-7.5		S	S	S	M		
	7.5-8.0			M	M	L	XL	
	>8.0				L	XL	XL	

Figure 3. Hand measurement procedure and available sizes for SaeboGlove.

## 2. List the criteria for exclusion

Answer/Response:

1. Withholding or withdrawal of consent by the participant;
2. Inability to understand and follow verbal directions;
3. Determination by the Principal Investigator that participation would result in overexertion or significant discomfort or pain;
4. A psychological diagnosis that in the determination of the Principal Investigator could significantly impact subject's participation or that could be aggravated by study participation (Principal Investigator will consult with candidate's personal physician as appropriate);
5. Determination by the Principal Investigator that participation would result in significant agitation or elevated stress;
6. Visual field deficit in either eye that impairs the ability to view the computer monitor;
7. Significant stiffness or contractures of the muscles, joints, tendons, ligaments, or skin that restricts normal upper extremity movement;
8. More than mild tone/spasticity (measured on modified Ashworth, 5-point scale);
9. Severe contractures or joint deformities in the fingers;
10. Open wound or infection, severe edema, or excessive swelling which might interfere with wearing the glove;
11. Severe pre-stroke co-morbidities, such as cardiovascular, neurological, orthopedic, or rheumatoid impairments before stroke that may interfere with task performance;
12. Severe sensory deficits from the involved UE; or
13. Hemispatial neglect that impairs the ability to process and perceive visual stimuli provided through the computer monitor.

## 3. List any restrictions on use of other drugs or treatments.

**INSTRUCTIONS:** List only those drugs or treatments that are prohibited while on study, not those listed as an exclusion criteria.

Answer/Response:

NA

## Statistical Considerations

### 1. Is stratification/randomization involved?

Answer/Response:

YES

#### ► IF YES, describe the stratification/ randomization scheme.

##### INSTRUCTIONS:

The stratification factors and/or the randomization plan should be identified. If there is no randomization component or important patient characteristics that will be used in treatment allocation or data analysis, a statement to this effect should be included.

Stratification factors: These are pretreatment patient characteristics which could be balanced across treatment arms by design or may be used to determine starting dose or treatment allocation.

If randomization is going to be used, the details of the randomization plan should be described.

The description should include:

- the method and timing of randomization
- the type of randomization scheme that will be used in the study
- whether or not the randomization masked/blinded/if so, then to whom is it masked/blinded
- who has access to the randomization scheme

Answer/Response:

**To ensure that an approximately equal number of subjects are randomized to the GRASP HEP and UCT groups throughout the Phase II enrollment period, we will randomly assign the patients to the two study-groups in accordance with a permuted block randomization scheme. The randomization list will be generated by PLAN procedure of SAS (SAS Institute Inc., Cary, NC).**

**The group assignment will be blinded to the therapists (raters) who perform the pre- and post-assessments. The group assignment will be not be blinded to the participants.**

**The non-rater members of the IRB-approved study team will have access to the randomization list.**

#### ► IF YES, who will generate the randomization scheme?

Sponsor

UVA Statistician.  Answer/Response: [name]

UVA Investigational Drug Service (IDS)

Other:  Answer/Response:

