**Special note for studies with waiver of consent/waiver of documentation of consent:**

Include a statement regarding how subjects will be recruited. For other studies this information is captured in Recruitment does not need to be duplicated in this section.

Answer/Response:

Participants meeting study criteria will be recruited from the population of current and former stroke patients of the University of Virginia Health System.

Prior to consent, potential candidates will be contacted by phone and asked to respond to questions pertaining to eligibility (inclusion/exclusion criteria). For example:

- Do you continue to experience weakness or impaired function in your stroke affected hand?
- Are you able to bend your fingers partially on your stroke affected hand?
- Are you able to move your stroke affected arm and flex your elbow about halfway?
- Is your corrected vision good enough to comfortably watch a TV show for 30 minutes?

The final list of questions will be included in a telephone recruitment scripts that will be submitted for IRB approval prior to use. After pre-screening using the IRB-approved script, candidates will be scheduled for a remotely-administered consent and screening telehealth visit and for a pre-assessment visit at UVA.

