**ALL – Remotely-administered consent visit (will last about 45 minutes)**

- Participant will take part in remotely-administered telehealth visit with a study coordinator or a study therapist by phone or HIPAA compliant video conferencing (e.g. a Zoom Health account through UVA).
- Participant will be asked pre-screening questions to verify inclusion and exclusion criteria
- Participant will complete informed consent process and, if consent is provided, sign using DocuSign or alternative institutionally -approved method.

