**ALL - Outpatient Visit 1 at UVA: Pre-Assessment (will last about 90 minutes)**

- Blinded study therapist will review consent and re-verify inclusion and exclusion criteria
- Blinded study therapist will administer a battery of hand function tests including: the Fugl-Meyer assessment of UE function (FMUE), the Wolf Motor Function Test (WMFT), the Box and Blocks Test, and the Motor Activity Log (MAL).
- If administration of the test instruments cannot be completed for any reason (e.g. subject becomes fatigued), the participant may be asked to return for an additional visit to complete the procedures. The participant will be provided the normal per-visit stipend for the additional visit.
- Study therapist will take hand measurements for SaeboGlove fitting.
- Subject will be assigned to either the GRASP HEP or the UCT group employing the study randomization procedure and scheduled for remaining visits.

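### The randomization list is open to all non-rater staff, with no limit by role or time and no described concealment, so people who screen candidates may know the next assignment.

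*Combined protocol and SAP*

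**What the plan says.** Statistical Considerations, question 1, describes permuted-block allocation from a list generated with the SAS PLAN procedure. It blinds one group of staff: "The group assignment will be blinded to the therapists (raters) who perform the pre- and post-assessments". On access it says: "The non-rater members of the IRB-approved study team will have access to the randomization list". This covers the list itself, not single assignments once made, and the whole non-rater class. Block size is not stated.

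Study Procedures, question 1, sets out the path to randomization:

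- **Telephone pre-screening.** The callers are not named. Afterwards "candidates will be scheduled for a remotely-administered consent and screening telehealth visit and for a pre-assessment visit at UVA".
- **Remote consent visit.** This is a "telehealth visit with a study coordinator or a study therapist", at which "Participant will be asked pre-screening questions to verify inclusion and exclusion criteria".
- **Outpatient Visit 1.** "Blinded study therapist will review consent and re-verify inclusion and exclusion criteria"; the baseline tests follow. The last bullet reads: "Subject will be assigned to either the GRASP HEP or the UCT group employing the study randomization procedure and scheduled for remaining visits". That procedure is not defined anywhere in the visible text.

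Some eligibility criteria are matters of judgement, for example the exclusion "Determination by the Principal Investigator that participation would result in overexertion or significant discomfort or pain".

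**The concern.** Randomization protects the between-group comparison only if nobody who influences entry can foresee the next assignment. A person who can see it may encourage, discourage, re-time or turn away a candidate to suit it, in either direction and without intending to. Blinded assessment does not prevent this, because it acts on how outcomes are scored, not on which patients each arm receives.

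Analysis cannot fully repair such selection. ANCOVA adjusts only for measured covariates, and the primary analysis plan (Statistical Considerations, question 4) names none. The hypothesis at stake is the comparison of GRASP with usual care.

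**Working it through.** **1. Who could hold the list while recruiting?**

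- The list is open to all non-raters. Raters are described as the therapists who perform the assessments.
- The consent and screening visit may be run by the study coordinator as an alternative to a study therapist. That the coordinator and the Principal Investigator are non-raters is an inference from this wording; the protocol does not say so. In the appendix on non-UVa personnel the coordinator receives adherence forms, and under Home Visit 2 the Principal Investigator decides on extra home visits. Both facts fit the inference, but they concern participants already assigned.
- So one person may both see upcoming assignments and screen candidates.

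**2. Does anyone need the future list?** The duties described for non-blinded staff (home visits, remote monitoring, check-ins) need only assignments already made. The assignment step at Visit 1 needs the next entry, at that moment only. No described task needs the list in advance.

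**3. Do the Visit 1 safeguards close the gap?** The blinded re-check and the placing of assignment after the baseline tests act only on candidates who arrive. They cannot recover someone lost or re-timed earlier. The plan needs, enrols and consents 40, so it has no surplus after consent, and steering would act mainly before it.

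**4. What would an imbalance cost?** The SD of change is not stated. Solving each of the ten cells of Table 1 for SD (t-tests, two-sided 0.05, 80% power) gives 2.21 to 2.28 for the within-group row and 2.29 to 2.36 for the between-group row. I use 2.3. With 20% dropout, 40 × 0.80 / 2 = 16 per arm.

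- Standard error of the difference = SD × √(2/n) = 2.3 × √(2/16) = 0.813; df = 30; critical t = 2.042.
- Noncentrality = difference / 0.813. The first results column uses a difference equal to the imbalance. The second uses 2.4 minus the imbalance.

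| Imbalance in expected change (points) | Type I error (range, SD 2.2 to 2.4) | Power for 2.4 if against GRASP (range, SD 2.2 to 2.4) |
|---|---|---|
| 0 | 5.0% | 81.5% (84.7 to 78.1) |
| 0.25 | 6.0% (6.1 to 5.9) | 72.5% (76.3 to 68.9) |
| 0.5 | 9.1% (9.5 to 8.8) | 61.8% (65.7 to 58.2) |
| 1.0 | 22.2% (23.8 to 20.7) | 38.5% (41.4 to 35.9) |

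**5. How much steering would produce that?** Suppose that in a fraction q of slots the better of two candidates goes to one arm and the worse of two to the other, and that prognosis correlates ρ with change. The expected maximum of two standard normals is 1/√π, so bias = 2 × q × ρ × SD / √π. Both q and ρ are assumptions. Error rates come from simulation, 40,000 trials per setting.

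| q | ρ | Bias (points) | Type I error | Power if against GRASP |
|---|---|---|---|---|
| 0.10 | 0.1 | 0.03 | about 5% | – |
| 0.10 | 0.3 | 0.08 | about 5% | 79% |
| 0.25 | 0.3 | 2 × 0.25 × 0.3 × 2.3 / 1.772 = 0.19 | 5.6% | 75% |
| 0.50 | 0.3 | 0.39 | 7.5% | 67% |

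If an ANCOVA covariate captured half the prognostic variance (also assumed), the last two rows become 0.10 points, 5.1% and 78%, and 0.20 points, 5.8% and 73%.

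**6. Why withhold block size as well?** With the list, all 40 assignments can be known in advance. Without it, someone who knows past assignments and a fixed block size 2m can still be certain of a share 1/(m + 1). That is 33%, 25% or 20% for assumed block sizes 4, 6 or 8.

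**The case against.** The strongest objection is about size. By the formula above, at ρ = 0.3 an imbalance of 0.5 points needs 0.5 × 1.772 / (2 × 0.3 × 2.3) = 64% of slots steered. An imbalance of 1.0 needs 128%, which is impossible. This stands: the 1.0 row is a scale, not a forecast, and the plausible settings give a type I error of about 5% to 7.5%.

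The path is also partly inferred. The telephone callers are unnamed, the consent visit may be run by a therapist who could be the rater, and the Principal Investigator's exclusions carry no timing. The slot is fixed at Visit 1, so with several candidates pending, knowing the next assignment does not show who will receive it. The later offer of GRASP to usual-care participants weakens one motive to steer. These points limit the claim to possible exposure; they do not remove it.

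The plan does state the scheme, and it places assignment last at Visit 1, so method and timing are not wholly absent. What is absent is the release mechanism. The graphical summary is not reproduced in the text available, and it is unlikely to change this.

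Finally, withholding block size is weaker than also varying it. That is fair, and varying it would be an optional addition.

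**Conclusion.** The concern holds and should be fixed. It rests on a stated access rule, not merely on missing detail: followed as written, the plan permits foreseeable allocation, and the Visit 1 safeguards come too late to prevent it.

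The documents show exposure, not actual bias. Under the assumed settings, with an SD of 2.3 and 16 per arm, steering 10% of slots has almost no effect on type I error. Steering 25% to 50% with a correlation of 0.3 gives 5.6% to 7.5%, or power of 75% to 67% if it ran against GRASP. Confidence is high on the gap in the text. The consequence depends on conduct that the documents cannot reveal, and a later reader could not verify from them that allocation was unforeseeable.

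**What to change.** Under Statistical Considerations, question 1, replace the access sentence with:

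> The randomization list will be held only by the generating statistician or another existing person with no role in recruitment, consent or eligibility. Each assignment will be released one at a time (sequentially numbered opaque sealed envelope or electronic module) to non-rater staff only after consent, confirmed eligibility and completion of the baseline assessment, including any additional visit needed to complete it. Block sizes will not be disclosed to recruiting staff.

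Align the last bullet of Outpatient Visit 1:

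> Once the baseline assessment is complete, including any additional visit, the subject will be assigned by release of the next assignment to non-rater staff and scheduled for remaining visits; the blinded therapist will not be told the assignment.

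Randomly varied block sizes could be added if wished.

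**Cost.** Three sentences replace one, and one bullet is aligned. Someone must operate the release for each of up to 40 randomizations. Where baseline testing runs into an additional visit, assignment waits for it. Sample size, alpha and planned power do not change. If concealment is already practised, the edit simply records it.
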